#### *6.2.1.1 Management of Daratumumab Reactions*

For reactions of any grade/severity, management may include but is not limited to treatment with acetaminophen, antihistamine, or corticosteroids. Intravenous saline may be indicated. For bronchospasm, urticaria, or dyspnea, patients may require antihistamines, oxygen, corticosteroids, or bronchodilators. For hypotension, patients may require vasopressors.

Management of reactions may further require treatment discontinuation of daratumumab as outlined below.

- Grade 1-2 (mild to moderate): Once reaction symptoms resolve, resume dosing at next scheduled dose interval.
- Grade 3 (severe): Once reaction symptoms resolve, resume dosing at next scheduled dose interval. Permanently discontinue daratumumab upon the third occurrence of a Grade 3 or greater infusion reaction.
- Grade 4 (life threatening): Permanently discontinue daratumumab treatment.

#### *6.2.1.2 Concomitant Medications*

##### Pre-injection Medications

Administer the following premedications to reduce the risk of reactions to all patients 1-3 hours prior to every SC injection of daratumumab.

- Dexamethasone 20 mg IV or PO. Dexamethasone must be given intravenously prior to the first daratumumab dosing and oral administration may be administered prior to subsequent injections.
- Antipyretic (oral acetaminophen 650 mg to 1000 mg)
- Antihistamine (oral or intravenous diphenhydramine 25-50 mg IV)
- Leukotriene receptor antagonist (oral montelukast 10 mg)
- If FEV1  $\leq$  80% at baseline, strongly consider administering  $\beta$ 2-adrenergic agonist inhaler (e.g. albuterol)

#### Post-injection Medication

Patients will be administered pre- and post-medications for the prevention and management of IRRs.

Consider administering low-dose oral methylprednisolone ( $\leq$ 20 mg) or equivalent day after daratumumab injection.

For patients with a higher risk of respiratory complications (eg, patients with mild asthma or patients with COPD who have an FEV1  $<$ 80% during screening or developed FEV1  $<$ 80% during the study without any medical history), the following medications should be considered following SC daratumumab injection:

- Antihistamine (diphenhydramine or equivalent)
- Short-acting  $\beta$ 2-adrenergic receptor agonist such as salbutamol
- Control medications for lung disease (eg, inhaled corticosteroids  $\pm$  long acting  $\beta$ 2-adrenergic receptor agonist for patients with asthma; long-acting bronchodilators such as tiotropium or salmeterol  $\pm$  inhaled corticosteroids for patients with COPD).

Please note that concomitant medications will be recorded in the medical record only.

#### 6.2.2 Pomalidomide Administration

Pomalidomide will be administered only to eligible patients under the supervision of the investigator or identified sub-investigator(s). Patients should be monitored for toxicity, as necessary, and doses of pomalidomide should be modified as needed to accommodate patient tolerance to treatment; this may include symptomatic treatment, dose interruptions, and adjustments of pomalidomide dose (see Section 6.3).

Pomalidomide will not be supplied for the study and will be obtained commercially.

Pomalidomide should be taken once daily at about the same time each day and may be taken with or without food.

The capsules should not be opened, broken, or chewed. Pomalidomide should be swallowed whole with water.

If a dose is missed, it may still be taken up to 12 hours after the time they would normally take it. If more than 12 hours have elapsed, they should be instructed to skip the dose for that day. The next day, they should take pomalidomide at the usual time. Warn patients not to take 2 doses to make up for the one that they missed.

#### 6.2.3 Clarithromycin (Biaxin®)

Clarithromycin is a semi-synthetic macrolide antibiotic and is active in vitro against a variety of aerobic and anaerobic gram-positive and gram-negative microorganisms. Biaxin® is indicated for the treatment of mild to moderate infections caused by susceptible strains of microorganisms. It is administered as 500 mg tablets (Abbott Laboratories) to be taken orally. It is rapidly absorbed after oral administration and distributes widely into most body tissue with the exception of the CNS. Peak serum concentrations within 2 hours with a Tmax of 2-4 hours. The elimination half-life is about 3 to 4 hours and has primarily renal excretion.

Commercial clarithromycin will be used. Subjects will receive a prescription from the investigator. 500 mg tablets for oral administration will be obtained from the subject's local pharmacy.

#### 6.2.4 Dexamethasone Administration

For Cycle 1, 20mg IV dexamethasone will be administered as a premedication on days 1 and 8 and 20 mg PO will be administered on days 2 and 9 (40mg weekly)\*\*; 40mg PO will be administered as premedication on days 15 and 22.

For Cycles 2-6, 40 mg PO dexamethasone will be administered weekly.

For Cycles 7-8, 20mg PO dexamethasone will be administered weekly.

For Cycle 9+, 20mg PO dexamethasone will be administered weekly.

When dexamethasone is administered on daratumumab treatment days, dexamethasone should be administered as a premedication prior to daratumumab injection.

\*\*Dexamethasone dosing if  $\geq 70$  years old- decrease dex dose by 50% in induction:

10 mg IV as premed on days 1 and 8 and 20mg PO on days 15 and 22 (Cycle 1)

10 mg PO the day after daratumumab on days 2 and 9 for Cycle 1 (total 20 mg/week)

20 mg PO as premedication weekly for cycle 2

20 mg PO weekly (cycles 3-6); 10 mg PO weekly (cycles 7+)

When taken orally, dexamethasone should be taken with food or milk to avoid gastrointestinal side effects. Missed doses can be taken as soon as the patient remembers if the next scheduled dose is 72 hours or more away. A double dose should not be taken to make up for a missed dose. If the patient vomits after taking a dose, the patient should not repeat the dose but should resume dosing at the time of the next scheduled dose.

#### *6.2.4.1 Prophylactic and Supportive Medications*

6.2.4.1.1. Valacyclovir 500 mg PO daily (or equivalent antiviral, renally dosed-adjusted), continuing for the duration of treatment (additional prophylaxis is at the Investigator's discretion) for varicella zoster prevention while on daratumumab and pomalidomide.

6.2.4.1.2 Aspirin 162 mg PO daily while on pomalidomide

6.2.4.1.3 Pantoprazole 40 mg PO daily, or other oral proton-pump inhibitor to prevent peptic disease for the duration of treatment with dexamethasone

6.2.4.1.4 IgG level will be checked monthly and IVIG (400 mg/kg) will be administered for IgG levels <500.

### **6.3 Dose-Modification Guidelines**

No daratumumab dose modification (increase or decrease) is permitted during the study. Guidelines for pomalidomide and dexamethasone dose modifications are provided in Sections 6.3.3 and 6.3.4, respectively, although are only guidelines and not intended to supersede the clinical judgment of the treating physician.

#### **6.3.1 Criteria for Beginning or Delaying a Subsequent Treatment Cycle**

Treatment with Daratumumab, Pomalidomide, and Dexamethasone will use a cycle length of 28 days. For a new cycle of treatment to begin, the patient must meet the following criteria:

- ANC must be  $\geq 1,000/\text{mm}^3$ .
- Platelet count must be  $\geq 75,000/\text{mm}^3$
- All other nonhematologic toxicity must have resolved to  $\leq$  Grade 2 or to the patient's baseline condition for cardiac toxicities (See Table 6.4 for definition of cardiac toxicities).

If the patient fails to meet the above-cited criteria for initiation of the next cycle of treatment, dosing should be delayed for 1 week. At the end of that time, the patient should be re-evaluated to determine whether the criteria have been met. If the patient continues to fail to meet the above-cited criteria, delay therapy and continue to reevaluate. The maximum delay before treatment should be discontinued will be 4 weeks or at the discretion of the Principal Investigator.

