## 4.3 Duration of Study

Patients will receive D-ClaPd at a dose defined by the treatment plan for up to 30 cycles, unless one of the following occurs:

- Disease progression
- Intercurrent illness that prevents further administration of treatment
- Unacceptable adverse event(s) defined as:

Occurrence of an AE that is related to treatment with the study drug which, in the judgment of the investigator, compromises the patient's ability to continue study-specific procedures, or is considered to not be in the patient's best interest.

Persistent AE requiring a delay of therapy for more than 4 weeks (28 days).

- Patient decides to withdraw from the study
- General or specific changes in the patient's condition render the patient unacceptable for further treatment in the judgment of the investigator
- Patient becomes pregnant
- Patient loses the ability to freely provide consent through imprisonment or involuntary incarceration for treatment of a psychiatric or physical illness
- Patient achieves complete remission (CR), and the patient and investigator feel that discontinuation is in the patient's best interests, or
- Patient achieves a level of response that qualifies him or her for another therapy, such as high dose therapy with autologous stem cell transplantation, and the patient and investigator feel that discontinuation is in the patient's best interests

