**Table 6-1 Daratumumab Dose Delay Schedule**

Cycles	Frequency	Dose Miss	Dosing Resumptio
1-2	Weekly (q1wk)	>3 days	next planned weekly dosing date
3-6	Every 2 weeks (q2wk)	>7 days	next planned dosing date
7-12	Every 4 weeks (q4wk)	>14 days	next planned monthly dosing date

**A missed dose will not be made up.** Doses of daratumumab given in Cycle 7 and onwards may be delayed up to 4 weeks. If a dose is delayed, then the dates of all subsequent doses must be adjusted. Any adverse event deemed to be related to daratumumab that requires a dose hold of more than 28 days will result in permanent discontinuation of daratumumab.

Patients whose dose is held for more than 28 days or are missing  $\geq 3$  consecutive planned doses of daratumumab for reasons other than toxicity should be withdrawn from study drug, unless, upon consultation with the PI and the review of safety and efficacy, continuation is agreed upon.

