#### Dosage Adjustment for Patients with Hepatic Impairment

For patients with mild or moderate hepatic impairment (Child-Pugh classes A or B), the recommended starting dose is 3 mg daily (25% dose reduction). For patients with severe hepatic impairment (Child-Pugh class C), the recommended dose is 2 mg (50% dose reduction)

Permanently discontinue pomalidomide for angioedema, skin exfoliation, bullae, or any other severe dermatologic reaction.

For other Grade 3 or 4 toxicities, hold treatment and restart treatment at 1 mg less than previous dose when toxicity has resolved to  $\leq$  to Grade 2 at the physician's discretion.

If pomalidomide is discontinued for toxicity, the patient may continue on study receiving daratumumab per study schedule with dexamethasone alone without pomalidomide.

Once pomalidomide is reduced for any toxicity, the dose may not be re-escalated.

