### **6.11 Termination of Treatment and/or Study Participation**

Patients will receive DPd at a dose defined by the treatment plan for up to 12 cycles, unless one of the following occurs:

- Hematologic disease progression.
- Intercurrent illness that prevents further administration of treatment
- Unacceptable adverse event(s) defined as:
  - o Occurrence of an AE that is related to treatment with the study drug which, in the judgment of the investigator, compromises the patient's ability to continue study-specific procedures, or is considered to not be in the patient's best interest.
  - o Persistent AE requiring a delay of therapy for more than 4 weeks (28 days).
- Patient decides to withdraw from the study
- General or specific changes in the patient's condition render the patient unacceptable for further treatment in the judgment of the investigator
- Patient becomes pregnant
- Patient loses the ability to freely provide consent through imprisonment or involuntary incarceration for treatment of a psychiatric or physical illness
- Patient achieves complete remission (CR), and the patient and investigator feel that discontinuation of DPd is in the patient's best interests, or
- Patient achieves a level of response that qualifies him or her for another therapy, such as high dose therapy with autologous stem cell transplantation, and the patient and investigator feel that discontinuation of DPd is in the patient's best interests.

Patients will be informed that they have the right to withdraw from the study at any time for any reason, without prejudice to their medical care. At the time of withdrawal, all study procedures outlined for the End of Study visit should be completed. The

primary reason for patient's withdrawal from the study should be recorded in the source documents and CRF.

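### After an adverse-event delay of more than 28 days, sections 4.3 and 6.11 end treatment, section 6.3.1 leaves it to the Principal Investigator, and nothing says which prevails

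*Combined protocol and SAP*

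**What the plan says.** Four sections of the protocol bear on a long delay.

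- **Section 4.3 (Duration of Study).** The lead-in reads "Patients will receive D-ClaPd at a dose defined by the treatment plan for up to 30 cycles, unless one of the following occurs". One listed item, under unacceptable adverse events, is "Persistent AE requiring a delay of therapy for more than 4 weeks (28 days". It carries no exception.
- **Section 6.11 (Termination of Treatment and/or Study Participation).** The same item appears, again without exception, under a different lead-in: "Patients will receive DPd at a dose defined by the treatment plan for up to 12 cycles, unless one of the following occurs".
- **Section 6.3.1 (starting or delaying a cycle).** A new cycle needs minimum neutrophil and platelet counts and recovery of non-hematologic toxicity. If these are not met, dosing is put back a week at a time. The section ends: "The maximum delay before treatment should be discontinued will be 4 weeks or at the discretion of the Principal Investigator".
- **Section 6.3.2 (text under Table 6-1).** An adverse event attributed to daratumumab that "requires a dose hold of more than 28 days will result in permanent discontinuation of daratumumab". The next paragraph concerns patients held for more than 28 days or missing three or more planned doses in a row. Its wording is "for reasons other than toxicity should be withdrawn from study drug, unless, upon consultation with the PI and the review of safety and efficacy, continuation"; the sentence closes by making this subject to agreement.

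Section 6.3.3, in the text on hepatic impairment, shows that partial discontinuation is foreseen for at least one drug: "If pomalidomide is discontinued for toxicity, the patient may continue on study receiving daratumumab per study schedule with dexamethasone alone without pomalidomide".

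**The concern.** A stopping rule for toxicity has to give the same answer whichever page the treating team opens. Here the strict lists in 4.3 and 6.11 and the discretionary limit in 6.3.1 give different answers for the same patient, and section 6.3.2 adds a further one when daratumumab is the suspected cause.

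Two things are at stake. The first is safety: the rule decides whether a patient who has not recovered after four weeks may be re-exposed. The second is consistent handling of the primary endpoint, which is the best response of VGPR or better within 8 cycles of a single-arm trial. Stopping or continuing changes exposure inside that window. It also changes the assessment schedule. Disease markers are measured every cycle on treatment, but every 90 days (plus or minus 30) for a patient who has stopped before progression and entered post-treatment observation. That affects when progression is detected, and so PFS and duration of response.

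**Working it through.** This is a comparison of texts; no stated figure depends on the rule.

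**Step 1. Do 4.3/6.11 and 6.3.1 cover the same situation?** The cycle-start criteria in 6.3.1 are blood counts and unresolved toxicity. Section 9.1.1 counts an abnormal laboratory value as an adverse event when it leads to a delay in treatment. A cycle held back under 6.3.1 is therefore held back by an adverse event. If it is still held after 28 days, it meets the item in 4.3 and 6.11. The situations coincide.

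**Step 2. Do they give the same consequence?** No. In 4.3 and 6.11 the regimen ends. In 6.3.1 the limit is four weeks or whatever the Principal Investigator decides, with no criteria and no upper bound.

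**Step 3. What does 6.3.2 add?** It applies only if the event is attributed to daratumumab. It ends daratumumab and does not mention pomalidomide, clarithromycin or dexamethasone. For such a patient whose whole cycle is also delayed, the possible outcomes are:

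- 4.3 and 6.11: the regimen ends.
- 6.3.1: treatment may continue at the Principal Investigator's discretion.
- 6.3.2: daratumumab ends; the other drugs are not addressed.

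**Step 4. Is the continuation clause in 6.3.2 clear?** No. The restriction to non-toxicity reasons follows two conditions joined by *or*: a hold of more than 28 days, and three or more consecutive missed doses. If it limits both, no agreed continuation exists for a toxicity hold. If it limits only the missed doses, any hold of more than 28 days can be continued by agreement, which collides with the sentence just before it on daratumumab-related events.

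**Step 5. Does any section take precedence?** None says so. The remark in section 6.3 that its contents are guidelines subject to clinical judgment is attached to pomalidomide and dexamethasone dose modifications, not to the stopping lists in 4.3 and 6.11.

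**Step 6. Is the design touched?** Inputs from section 8.1.1: n = 40, success at 8 or more, null rate 9%, target rate 25%. With X binomial:

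- alpha = P(X ≥ 8 | 40, 0.09) = 0.0242, within the stated 5%;
- power = P(X ≥ 8 | 40, 0.25) = 0.818, above the stated 80%.

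The plan's figures reproduce, and the delay rule does not enter them.

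**The case against.** The strongest reply is that the sections differ in scope: 4.3 and 6.11 concern delay of therapy, 6.3.1 the start of a cycle, and 6.3.2 a hold of one drug. Stopping one drug while others continue is an accepted path, as section 6.3.3 shows for pomalidomide. This stands in part. It largely explains 6.3.2, and the three outcomes in step 3 arise only when a daratumumab-related event also delays the whole cycle. It does not explain 4.3 and 6.11 against 6.3.1, because both concern treatment as a whole.

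Several stronger readings are tempting, and the documents do not support them.

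- *Any delay beyond 28 days ends all treatment.* The item in 4.3 and 6.11 covers persistent adverse events only. Holds for stem cell collection, for example, have their own four-week limit in section 7.5.
- *Such delays will be common.* A reader might cite the 78% rate of grade 3 or higher neutropenia with daratumumab, pomalidomide and dexamethasone (section 1.1) or the 67% rate of pomalidomide interruption (section 1.4.2). Neither measures a delay of more than 28 days, and Table 6-3 handles many such events within the cycle. The background discontinuation rates (3%, 8% and 15% in different studies) do not measure it either.
- *One discretionary continuation could turn 7 responders into 8 and reverse the result.* Exactly 7 of 40 has probability 0.0639 − 0.0242 = 0.040 at a true 9% and 0.9038 − 0.8180 = 0.086 at 25%, where 0.0639 and 0.9038 are the probabilities of 7 or more. The reversal also needs a long delay in induction, a discretionary continuation, and a first VGPR only afterwards. A VGPR reached before the delay counts in any case, and stopping treatment does not remove a patient from the full analysis set.
- *The discretion in 6.3.1 is what makes continuation depend on response.* Investigator judgment over stopping is already written into other items of 4.3 and 6.11, so aligning the 28-day wording would not remove it.

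**Conclusion.** The contradiction is real and the text is wrong as written: for an adverse-event delay of the next cycle beyond 28 days, 4.3 and 6.11 cannot both be followed to the letter if the discretion in 6.3.1 is used. Section 6.3.2 adds an unresolved question about the remaining drugs and an ambiguous continuation clause.

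The effect falls on safety handling, on exposure within the 8-cycle window, and on the assessment schedule after stopping. Its size is unknown, because the number of patients affected cannot be estimated from the documents. Sample size, the 8-of-40 rule and the nominal error rates are unchanged. The conclusion rests on two readings: that the list in 4.3 ends all study treatment, which its other entries (such as progression and pregnancy) support, and that a count-driven cycle delay is an adverse event, which section 9.1.1 supports.

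**What to change.** Reconcile sections 4.3, 6.3.1, 6.3.2 and 6.11 into one statement of what happens when an adverse event delays treatment by more than 28 days. It should say:

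- which drugs stop, with the daratumumab-related case treated explicitly;
- whether Principal Investigator discretion applies, and to which cases;
- whether the non-toxicity restriction in 6.3.2 limits both the long hold and the missed doses.

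The other sections should then refer to that statement instead of restating it. The same edit should reconcile the lead-ins of 4.3 and 6.11, which name different regimens and different maximum numbers of cycles. The clinical rule itself is for the sponsor.

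If discretion is kept, a listing of patients continued past 28 days with their best response would let a reader see how often it was used. That is optional. The cost is protocol wording and, if adopted, one listing.

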### 6.3.2 Daratumumab Dose Modifications and Delays

No daratumumab dose modification (increase or decrease) is permitted.

During each cycle, the daratumumab dose must be held if any of the following criteria are met, to allow for recovery from toxicity.

- Grade 4 hematologic toxicity, or Grade 3 or higher thrombocytopenia with bleeding;
- Grade 3 or higher non-hematologic toxicities with the following exceptions:
  - Grade 3 nausea or Grade 3 vomiting that responds to antiemetic treatment,
  - Grade 3 diarrhea that responds to antidiarrheal treatment,
  - isolated Grade 3  $\gamma$ -glutamyltransferase elevation, or
  - Grade 3 fatigue or asthenia that was present at baseline or that lasts for <7 days after the last administration of daratumumab.

Daratumumab treatment should be resumed when the toxicity has resolved to  $\leq$  Grade 2. If the daratumumab administration does not commence within the prespecified window of the scheduled administration date as per Table 6-1, then the dose will be considered a missed dose. Administration may resume at the next planned dosing date.

**Table 6-1 Daratumumab Dose Delay Schedule**

Cycles	Frequency	Dose Miss	Dosing Resumptio
1-2	Weekly (q1wk)	>3 days	next planned weekly dosing date
3-6	Every 2 weeks (q2wk)	>7 days	next planned dosing date
7-12	Every 4 weeks (q4wk)	>14 days	next planned monthly dosing date

**A missed dose will not be made up.** Doses of daratumumab given in Cycle 7 and onwards may be delayed up to 4 weeks. If a dose is delayed, then the dates of all subsequent doses must be adjusted. Any adverse event deemed to be related to daratumumab that requires a dose hold of more than 28 days will result in permanent discontinuation of daratumumab.

Patients whose dose is held for more than 28 days or are missing  $\geq 3$  consecutive planned doses of daratumumab for reasons other than toxicity should be withdrawn from study drug, unless, upon consultation with the PI and the review of safety and efficacy, continuation is agreed upon.

